Data collection. The program manager (PM) will track recruitment and retention. A clinical assessor will conduct diagnostic interviews and questionnaire evaluations pre-, mid-, and post-intervention blind to group allocation. All pre-, mid-, and post-treatment biological measures will be conducted and analyzed by the psychophysiological and consultants, blind to group allocation.

Assessment, Data Collection, and Schedule. Instruments and other data collection tools and their description are in the [Assessment Detail](#). This strategy includes repeat measures yet minimizes response burden. Our goal is to test for effect signal. It is premature to evaluate durability and not ethical to keep subjects in a protocol where they may not be receiving effective treatment (particularly true of MIN), so we will not include a six-month follow-up period. Instead, a one-month follow-up will test symptoms and functioning and be utilized to re-connect participants to clinical services. Data collection at mid-point of treatment is warranted to replicate mid-treatment findings from our first trial. Such a finding may help determine dose effects and plan a dose-finding trial.

Outcome measures. The primary outcome is change in PTSD symptom severity from pre- to post-treatment. We hypothesize a large pre- to post-treatment effect for ACU ($d \geq 0.8$) and at least a mild treatment effect ($d \geq 0.30$) of the difference between groups (ACU vs MIN) pre- to post-treatment, with 80% probability of detecting a true group difference at $p < 0.05$ (2-sided). Main biological outcome (secondary outcome) is change from pre- to post-treatment in PPR (decreased startle by EMG eyeblink).

IV. Statistical Plan and Data Analyses

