General Approach. General linear mixed models (GLMM) are capable of handling multiple underlying distribution and model structures through link functions, such as repeated measures random effects models of continuous outcomes (identity link), repeated measures logistic models (logit link), and Poisson and negative binomial models (log link). In addition to modeling global fixed effects across subjects, GLMM can also model individual subject random effects. Survival analysis allows for the assessment of time to event modeling using probability estimates on survivor functions and estimates of hazard ratios. Time to event modeling using Cox proportional hazard modeling allows for all subjects to contribute information to the model up until occurrence of event, drop out, or end of study. Cox Proportional Hazards modeling will be used to investigate for effect-size of the treatment by allowing subjects to contribute their information to the model while they are being observed and censored once they are no longer being observed (loss to follow-up or end of study period). Further, using the Cox modeling we will investigate for time dependencies and informative loss to follow-up. In the case where dropouts may be associated with the treatment assignments, we will leverage intention to treat methodology and construct a piecewise random effects model with both "on-" and "off-treatment" slopes. GLMM will be used to evaluate the primary clinical hypothesized effects of treatment (ACU) on the clinical outcome of PTSD symptom severity (CAPS) over time (mid- and end-treatment, and 1-month follow-up), controlling for baseline severity of symptoms and demographic characteristics (e.g., age, gender) in comparison with placebo control group (MIN) with assumption of intent to treat. Cohen's *d* within and between subjects will be calculated. Interaction terms will be included in the models to evaluate treatment fidelity and treatment expectancy as potential moderators.

GLMM will also be used to evaluate the secondary biological hypothesized effects of treatment on pre- to post-treatment in PPR (decreased EMG eyeblink). These same statistical procedures (GLMM, survival analysis, and Cohen's *d* with intent to treat) will be applied to evaluate exploratory outcomes: clinical symptoms comorbid with PTSD, PPR (HR, HRV, SCR), and PTSD diagnosis.

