Statistical Analyses, Primary Hypothesis. Prior to the application of any statistical modeling, underlying assumptions and conditions will be examined. Univariate analyses, including tests of distribution assumptions, t-tests, and chi-square tests will be conducted to determine possible significant covariates to be included in further multivariable modeling as well as to investigate efficiency of randomization techniques. All models will be assessed for goodness of fit as well as other diagnostics including assessment for collinearity performed on all covariates chosen for subsequent analyses. Repeated measures analysis of variance will be used to formally test the null hypothesis of no differences in baseline PTSD symptom mean levels and subsequent retest of PTSD symptom mean levels while simultaneously adjusting for any significant covariates. All models will be run accounting for any potential confounders. Analyses will be performed assuming intent to treat and informative loss-to-follow up will be investigated. Additional analyses will be conducted to determine interactions and mediating effects while simultaneously adjusting for other covariates in the model.

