Assumptions for Power Calculations. Assumptions are based on interpolated data since primary outcomes in our first ACU study were assessed with the PSS-SR scale and there are no PTSD studies using MIN as the sham. Furthermore, to be consistent with major PTSD research, we will use the CAPS-5 (DSM-5 version) as the primary outcome, and there are as of yet no completed clinical trials using CAPS-5. In our first study, mean pre-treatment PTSD severity score was about 62% of maximum (31.55 of 51). ACU mean decreased 50% - 31.33 (10.1) to 15.65 (13.95) and wait-list mean decreased 9.3% - 30.79 (9.54) to 27.92 (12.33) at post-treatment. We thus assume that subjects will have a baseline mean CAPS-5 score of 50 (10) and a 50% reduction of symptoms and a 38% increased variance (CAPS-5 = 25; SD = 13.8) with ACU. There are sparse data about effects of MIN, noting a 33% improvement compared to pharmacological treatment only, and a 33% less effect than ACU in the Shen study. A 2010 Cochrane systematic review of over 200 trials investigating 60 clinical conditions about general placebo effect found placebos to not have important clinical effects but may influence patient-reported outcomes in some situations (e.g., pain and nausea). The pooled relative risk calculated for placebo was 0.93 (effect of only 7%) but significant. Confidence intervals are generally wide in the placebo arm. Several clinical and methodological factors were associated with higher effects of placebo. Since our study

includes some of these factors, and since we expect MIN to have some physical effect, MIN could provide an effect as much as 33% with a wider variance. This would predict mean CAPS-5 scores (MIN) at end-treatment of 33.5 (SD 15). The conservative prediction is mean CAPS-5 reductions of 25 points with ACU and 16.5 points with MIN, an 8.5-point difference with a pooled SD of 14.4. Given our experience and data about placebo effect, we can modestly expect a 12 point between group CAPS-5 difference and a pooled SD of 15.

Treatment Effects, Power and Sample Size, Primary Hypothesis. “The efficacy of verum acupuncture (ACU) for PTSD symptom severity will be large (pre- to post-treatment Cohen’s $d \geq 0.8$), and significantly better than sham acupuncture (MIN) (between group Cohen’s $d \geq 0.30$, with 80% probability of detecting a true group difference at $p < 0.05$ (2-sided).”

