Effects. The conservative assumptions noted above will result in pre- to post-treatment Cohen’s $d = 2.07$ within group (ACU) and between group (post-treatment difference) Cohen’s $d = 0.59$, which will prove the null hypothesis false and show a large treatment effect for ACU and a moderate between-group effect size.

Sample size needed and power. The conservative assumptions would require a total of 90 patients in a two-treatment parallel-design to provide a probability of 80 percent to detect a treatment difference at a two-sided 0.05 significance level. Modest assumptions of a 12-point difference with a pooled SD of 15 requires a total of 50 patients with power of 0.80 at $\alpha < 0.05$.

This was determined using a formula for a random effects modeling (Montgomery, 1991), which may determine the necessary sample size to detect a statistically significant difference in treatment/control group means at different levels of projected effect differences.

$$n = \frac{2 * a * M^2 * \Phi^{*2}}{\Delta^2}$$

Where:

M = measure of noncentrality parameter to estimate the standard normal probability of making a type II error

n = number of replicates necessary for each treatment

a = number of treatments (a=2)

Φ^* = estimated standard deviation

Δ = difference in baseline and post treatment

Table. Examples of sample sizes necessary for significance testing at different mean and SD’s (between group: treatment (ACU) and control (MIN)) for PTSD severity (primary outcome) at power = 0.80.

Mean difference between ACU and MIN PTSD severity scores post-treatment	Φ^2	Total N Using Formula Above
8.5	12	62
	14.4	90
	15	96
	20	162
12	12	32
	15	50
	20	86

Recruitment goals are N=90, 45 per group. With a post-randomization attrition rate of 10% we will have at least 40 individuals in each group. Considering attrition, the above table indicates that for an average difference in means of 12 at end-treatment with a standard deviation of 15, a total sample size of 50 (25 in each group) would be more than adequate to report a statistical difference with 80% power. If differences in treatment group means were found to be larger than 12, we would need even fewer subjects in our treatment groups to achieve statistical significance.

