Note: One task of Data Safety and Monitoring on funding will be to review the protocol and advise the investigators about rules for continuation or discontinuation of each subject in the study and in the follow-up period. It may be unethical to continue Veterans in the follow-up period if there is no pre- to post-treatment reduction in CAPS. Furthermore, we are most interested in whether there is effect maintenance in those who have responded to treatment, so it may be scientifically meaningless in addition to the ethical dilemma to continue non-responders into the follow-up period. In this A1 revision, our primary goal is to determine if ACU provided effect (signal) compared to a placebo, and the follow-up period is not to primarily determine durability of treatment but to ensure safety and clinical follow-up planning. Our statistical methods will be able to manage data in an intent-to-treat model if subjects are withdrawn. Our current plan is to define a response as a CAPS-IV equivalent drop of 10 points (the value for CAPS-5 still needs to be determined). Those who have not had a response would have the option to withdraw and re-initiate clinical treatment immediately. Of course, any subject may withdraw at any time.

Description of Intervention Protocols

Recruitment of participants currently on medications for PTSD. It may be ideal to recruit subjects who are medication naïve, but this is not feasible in this single site study. Approximately 55% of Veterans with PTSD who are entering three of our current studies (a DoD funded multi-site trial of prolonged exposure with vs without virtual reality, [name] PI, [name], Long Beach site PI; a VA national cooperative studies program comparing prolonged exposure to cognitive processing therapy – CSP #591, [name] et al PI's, [name] Long Beach site PI and executive committee member; an industry sponsored two-site RCT of Vilazodone vs. placebo for PTSD, [name] and [name] Co-PI's) are on a medication when entering the trial, most often an SSRI. In the first two mentioned studies, the subjects can stay on the medication (with rules), and for the third study we offer a wash-out if the current medication has not been established for a long period or if effects are neutral or negative. We will thus offer a similar procedure in the proposed study to the first two mentioned studies, and the subject must be on a stable dose for 8 weeks or longer.

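### The primary hypothesis is a defined ACU-versus-MIN comparison, but the only test called formal compares baseline with retest and names no arm, and the mixed model against MIN designates no visit or contrast

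*Protocol*

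**What the plan says.** **The target.** Protocol, Outcome measures, makes pre- to post-treatment change in PTSD severity the primary outcome. It sets a within-ACU effect of d ≥ 0.8 and an effect of d ≥ 0.30 "of the difference between groups (ACU vs MIN) pre- to post-treatment", tested two-sided at 0.05. The primary hypothesis, in the power section of both documents, has ACU "significantly better than sham acupuncture (MIN"). The sample-size table is indexed by "Mean difference between ACU and MIN PTSD severity scores post-treatment". The note on the follow-up period in Clinical Protocol Detail says "our primary goal is to determine if ACU provided effect (signal) compared to a placebo".

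**The formal test.** Under Statistical Analyses, Primary Hypothesis (protocol section IV, and the same heading in the SAP), one test is called formal. It is a repeated measures ANOVA to "formally test the null hypothesis of no differences in baseline PTSD symptom mean levels and subsequent retest of PTSD symptom mean levels", adjusted for whichever covariates prove significant in univariate screening. The sentence names no arm, no group-by-time term and no retest visit.

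**The other model.** The General Approach paragraph, which comes before it in both documents, assigns the primary clinical effect to a mixed model (GLMM) in comparison with MIN, "over time (mid- and end-treatment, and 1-month follow-up), controlling for baseline severity of symptoms and demographic characteristics (e.g., age, gender"). No visit or contrast is singled out. Neither paragraph says which of the two analyses is confirmatory, and the SAP repeats both without settling it.

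**The concern.** The claim the trial wants to make is that verum beats sham. A test of baseline against retest asks whether scores moved over time. Both arms are expected to improve, so a significant result would be compatible with ACU and MIN being identical.

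If the analyst sets that sentence aside and uses the mixed model, the comparator is right but the contrast is still open. It could be the end-treatment difference, an average over mid-treatment, end-treatment and 1-month follow-up, or a group-by-time effect over all visits. Each answers a slightly different question. If the choice is made after seeing results, the nominal 5% no longer holds. The sample size rests on just one of these, the post-treatment difference between arms.

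**Working it through.** **Step 1. What N = 90 was computed for.** Inputs from the power section: ACU end-treatment SD 13.8, MIN SD 15, reductions of 25 and 16.5 points, two-sided 0.05, power 0.80.

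- Difference: 25 − 16.5 = 8.5. Pooled SD: √((13.8² + 15²)/2) = 14.4. Between-group d: 8.5/14.4 = 0.59, as stated.
- The plan's formula, with a = 2 and M taken as 1.96 + 0.842 = 2.802 (no value of M is given): 2 × 2 × 2.802² × 14.4² / 8.5² = 90.1. The table prints 90 as total N.

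The trial is therefore sized on a two-arm comparison at post-treatment, not on a time test.

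**Step 2. The formal test read literally.** Suppose ACU is no better than MIN and both arms fall by the plan's sham figure of 16.5 points. Baseline SD is 10 and end-treatment SD is 15 (plan). The pre-post correlation r is not given and is assumed to be 0 to 0.7.

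SD of change = √(10² + 15² − 2r × 10 × 15); noncentrality = 16.5 × √N / SD of change.

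| r | SD of change | Noncentrality, N = 80 | Noncentrality, N = 90 |
|---|---|---|---|
| 0 | 18.0 | 8.2 | 8.7 |
| 0.5 | 13.2 | 11.2 | 11.8 |
| 0.7 | 10.7 | 13.8 | 14.6 |

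The two-sided critical value is about 2, so rejection exceeds 99.9% in every case. In a simulation of 90 patients at r = 0.5 with equal arms, the time test rejected in 100% of trials and the group-by-time test in 4.9%.

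**Step 3. Illustration of an open contrast.** Take ACU = MIN and two tests that could be drawn from the text:

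- Test A: two-sample t-test on end-treatment change.
- Test B: group effect on the mean of mid-treatment, end-treatment and 1-month scores, adjusted for baseline.

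Assumptions: SD 10 at baseline and 15 at all three later visits (the plan supports 15 only for MIN at end-treatment), complete data, 40,000 trials per cell. Each test alone rejects in 4.8-5.2% of trials. The chance that at least one rejects is:

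| Correlation pattern | n per arm | r = 0.3 | r = 0.5 | r = 0.7 |
|---|---|---|---|---|
| Equal between visits | 40 | 8.5% | 8.4% | 8.1% |
| Equal between visits | 45 | 8.6% | 8.2% | 8.0% |
| AR(1), adjacent r | 40 | 8.7% | 7.8% | 7.2% |
| AR(1), adjacent r | 45 | 8.6% | 8.0% | 7.2% |

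**Step 4. Does naming the end-treatment contrast change N?** The unadjusted comparison has power 0.80 at 45 per arm, which is the plan's own calculation, and 0.75 at 40 per arm. Adjusting for baseline multiplies the SD by √(1 − r²). Power for r = 0.3 / 0.5 / 0.7 is then 0.84 / 0.90 / 0.98 at 45 per arm and 0.79 / 0.86 / 0.96 at 40. The basis for N = 90 does not move.

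**The case against.** The strongest reply is that nobody could mistake the intent. Outcome, comparator, time window, alpha and sidedness are all written down, the sample size uses the post-treatment difference between arms, and the General Approach assigns the primary effect to a model against MIN. That paragraph also counts repeated measures models among the GLMMs, so the ANOVA sentence may be a loose description of the same analysis. Or it may serve the within-ACU part of the hypothesis.

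Much of this stands, and it rules out several stronger readings:

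- A reader might infer that the trial has no between-arm hypothesis or no primary time point. It has both.
- A reader might infer that no ACU-MIN analysis is planned. One is planned; it is not fixed as the confirmatory test.
- A reader might infer from the formula's definition of Δ, "difference in baseline and post treatment", that the trial is powered on a time effect. Step 1 shows that the figure of 90 comes from the 8.5-point difference between arms.
- A reader might take the 99.9% as a false-positive rate for superiority to sham. It is power against a time null that really is false, and shows only that this test does not address the claim.
- A reader might take 7-9% as the plan's type I error. The two tests in Step 3 were constructed for illustration, and the excess arises only if the better result is picked afterwards. The plan does not say it will do that.

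What the reply does not remove is that neither analysis paragraph, in either document, states the test that matches the target. If the ANOVA was meant only for the within-ACU effect, the paragraph on the primary hypothesis contains no between-arm test at all.

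**Conclusion.** The point holds as a gap between a defined target and the analysis text. The one test called formal, taken as written, asks the wrong question for the primary claim. The model that asks the right one is left without a visit, a contrast or a rank. This rests on the wording alone and needs no numerical assumption.

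The numbers are secondary. The near-certain significance of the time test depends on the plan's 16.5-point sham assumption and holds for any assumed correlation from 0 to 0.7. The 7-9% is illustrative and depends on the assumed correlations, the assumed SD at mid-treatment and 1-month, complete data, and selection after the fact. It should be corrected before unblinding. It does not call the design or N = 90 into question.

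**What to change.** In both protocol and SAP, replace the ANOVA sentence with wording such as:

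> The confirmatory between-group test is the ACU minus MIN difference in CAPS-5 total at end-treatment, from the planned mixed model (group, visit, group-by-visit, baseline CAPS-5, and a covariate list fixed before unblinding) in all randomised subjects, two-sided alpha 0.05. Mid-treatment and 1-month contrasts, and models with covariates chosen by univariate tests, are supportive.

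The group-by-visit term is an addition; it lets the end-treatment difference be read from a three-visit model. The sponsor should settle the covariate list in advance. Age and gender appear in the General Approach only as examples, and the minimization factors (combat exposure, pre-deployment preparedness, gender) should be considered for it.

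Add one sentence saying that the within-ACU pre- to post-treatment effect (d ≥ 0.8) is reported separately and cannot substitute for the between-group test.

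The cost is wording in two documents. The model and visits are already planned, no new data are needed, and N = 90 stays. The labels in the sample-size formula and the piecewise on/off-treatment model for dropout are separate matters and are not part of this change.

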This is a 5-year study at the Long Beach VA Healthcare System (LBVA). Collaborating partners within the LBVA are The Program for Traumatic Stress' Novel Therapies Unit developed and directed by PI [name]; the Integrative Medicine Clinic founded and directed by Co-I [name] PhD; the Research Healthcare Group led by [name] MBA; and the PTSD psychophysiology laboratory managed by [name]. External collaborating partners include our design and analytic experts [name] from UCSD and National University and [name], Chair of Community Health at National University; the developers of our psychophysiology laboratory [name] and [name] from Emory University and the Atlanta VA.

[figure not shown]
Design. A two-arm, parallel-group, prospective randomized placebo controlled clinical trial to evaluate the efficacy of acupuncture for PTSD.

Study Timeline. Start-up and final IRB approvals will be completed by month 6. Subjects will be accrued at 2.5 per month from study month 7 to 44. All subjects will complete treatment by month 47 and follow-up assessment by month 48. Analyses for primary hypothesis and all reports will be completed by month 57.

Participants and sampling. The sample frame is Veterans with chronic PTSD due to combat exposure seeking treatment at the LBVA or affiliated programs. The figure shows the flow of the project. Withdrawals prior to beginning intervention will be replaced. The sample size (90) provides adequate power to test primary hypothesis.

Inclusion criteria are meant to recruit a relatively homogeneous yet generalizable sample of Veterans with at least moderate chronic PTSD due to combat trauma. Criteria are: (1) Veterans aged 18 to 55, (2) DSM-5 criteria for chronic PTSD on the Clinician Administered PTSD Scale (CAPS-5), and (3) at least moderate PTSD by having a total CAPS-5 score of ≥ 26 and meeting criteria for each of 4 symptom clusters. Eligible persons will be allowed to have other symptoms that are commonly comorbid with PTSD (e.g., anxiety, mild to moderate depression), but these will not be inclusion or exclusion criteria. This strategy will provide a feasible and

Figure. Sample Frame and Flow of Project

generalizable sample of those with chronic PTSD. Women and minorities will be recruited.

Definition of “PTSD due to combat trauma:” Subjects must have PTSD due to a traumatic event in a combat zone. This may be any type of trauma, AND PTSD may be complex (i.e., combined war event, sexual event, MVA, etc).

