Aggression Questionnaire (Buss et al, 1992)	weekly		X	X	X
Beck Depression Inventory – II items 9, 11, 17	weekly				
Satisfaction with Care and Provider Scale (Unpublished)			X		X
Intercurrent Health Resource Use Inventory	X		X		X
6. Treatment Fidelity and Expectancy					
Treatment Fidelity Assessment (Therapist Adherence Scale)	selected				
The Credibility Rating Scale (Borkovec, 1972)	selected				

Description of Instruments

1. Screening and Diagnostics

The Clinician Administered PTSD Scale (CAPS) (Blake et al, 1995) is a structured diagnostic interview for PTSD. The new CAPS-5 based on DSM-5 criteria will be used (CAPS-5 update, unpublished: Weathers et al, 2013). As with previous versions of the CAPS, CAPS-5 symptom severity ratings are based on symptom frequency and intensity, except for items 8 (amnesia) and 12 (diminished interest), which are based on amount and intensity. However, CAPS-5 items are rated with a single severity score, in contrast to previous versions of the CAPS which required separate frequency and intensity scores for each item that were either summed to create a symptom severity score or combined in various scoring rules to create a dichotomous (present/absent)

symptom score. CAPS-5 has 20 symptom items, each rated from 0 (absent) to 4 (severe). A rating of >2 is considered a positive score for diagnostic purposes. There are 4 symptom clusters: the Criterion B (re-experiencing) severity score is the sum of the individual severity scores for items 1-5; the Criterion C (avoidance) severity score is the sum of items 6 and 7; the Criterion D (negative alterations in cognitions and mood) severity score is the sum of items 8-14; and the Criterion E (hyperarousal) severity score is the sum of items 15-20. The DSM-5 diagnostic rule requires the presence of least one Criterion B symptom, one Criterion C symptom, two Criterion D symptoms, and two Criterion E symptoms in addition to other impairment criteria (see “scoring” on CAPS). A DSM-5 CAPS cutoff score of ≥ 26 AND meeting each of the 4-symptom cluster criterion will be used for study inclusion. This is consistent with what will be used in the VA Cooperative Study #591, which is the first national study to use the CAPS-5 for diagnosis and treatment effect assessment.

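### The pilot mean was moved to the CAPS-5 scale but its SD was not, so d = 0.59 and 80% power at N = 90 are not supported by the plan's own evidence

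*Protocol*

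**What the plan says.** The sample-size reasoning is in the Protocol, section IV, under Assumptions for Power Calculations and the two paragraphs after it. The SAP repeats it with the same figures.

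- Source: "Assumptions are based on interpolated data since primary outcomes in our first ACU study were assessed with the PSS-SR scale".
- Pilot baseline: "mean pre-treatment PTSD severity score was about 62% of maximum (31.55 of 51").
- Pilot acupuncture arm: "ACU mean decreased 50% - 31.33 (10.1) to 15.65 (13.95").
- Pilot control arm: "wait-list mean decreased 9.3% - 30.79 (9.54) to 27.92 (12.33) at post-treatment".
- Planning assumption: "We thus assume that subjects will have a baseline mean CAPS-5 score of 50 (10) and a 50% reduction of symptoms". The acupuncture SD after treatment is then set at 13.8.
- Sham arm (MIN): 33.5 with SD 15 after treatment. The SD is chosen by judgement as somewhat wider.
- Result: a difference of 8.5 points, pooled SD 14.4, between-group d 0.59 and within-group d 2.07.
- Sample size: "The conservative assumptions would require a total of 90 patients in a two-treatment parallel-design to provide a probability of 80 percent". A second scenario, 12 points with SD 15, is said to need 50.

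The Protocol's Participants and sampling paragraph concludes: "The sample size (90) provides adequate power to test primary hypothesis". The Assessment Detail fixes the scale maximum: "CAPS-5 has 20 symptom items, each rated from 0 (absent) to 4 (severe"), so 20 × 4 = 80. The power section also says that no trial using CAPS-5 had yet been completed.

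**The concern.** The mean and the SD appear to be on different scales. The remark that the pilot mean was 62% of maximum serves only to carry the mean to a scale with another maximum, and 62% of 80 is 49.6. Nothing comparable was done to the SD. Differences in CAPS-5 points are therefore divided by an SD that is in effect in PSS-SR points, and every standardised effect is enlarged by roughly 80/51.

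The error reaches the primary hypothesis. If the trial's power for the difference it calls conservative is nearer one half than 80%, a non-significant result could be read as evidence against acupuncture when the trial had a large chance of missing that effect.

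**Working it through.** **1. Reproduce the plan.** Pooled SD = √((13.8² + 15²)/2) = 14.4. Between-group d = 8.5/14.4 = 0.59. Within-group d = 25/√((10² + 13.8²)/2) = 25/12.05 = 2.07. Total N = 4 × (1.96 + 0.84)² × SD²/Δ² = 4 × 7.849 × 14.4²/8.5² = 90.1. Power at 45 per arm is 80% by the normal approximation and 79% by the t distribution. The arithmetic is sound, so the question is the input SD.

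**2. Trace the inputs.**

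| Quantity | Pilot (PSS-SR, max 51) | Plan (CAPS-5, max 80) | Rescaled? |
|---|---|---|---|
| Baseline mean | 31.55 (61.9% of max) | 50 (0.62 × 80 = 49.6) | yes |
| Baseline SD | 10.1 | 10 | no |
| Acupuncture SD, post | 13.95 (ratio to baseline 1.38) | 13.8 (10 × 1.38) | no |
| Control SD, post | 12.33 (wait-list) | 15 (sham, judgement) | no pilot value used |

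**3. Internal check.** The pilot's within-group d, computed the same way, is (31.33 − 15.65)/√((10.1² + 13.95²)/2) = 15.68/12.18 = 1.29. The plan assumes the same 50% fall and the same SD ratio, yet obtains 2.07. The inflation is 2.07/1.29 = 1.6, close to 80/51 = 1.57. The remainder comes from rounding 49.6 to 50 and 10.1 to 10.

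**4. Put the SD on the scale of the mean.** This assumes proportional scaling by 80/51.

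- Pilot post-treatment SDs: √((13.95² + 12.33²)/2) = 13.16, and 13.16 × 1.569 = 20.65.
- The plan's pooled SD: 14.4 × 1.569 = 22.6.

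Results for 8.5 points, two-sided 0.05, unadjusted (power from the t distribution, N from the formula in step 1 rounded up per arm):

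| Pooled SD | d | Power, 45 per arm | Power, 40 per arm | Total N for 80% |
|---|---|---|---|---|
| 14.4 (plan) | 0.59 | 79% | 74% | 92 |
| 20.65 | 0.41 | 49% | 44% | 186 |
| 22.6 | 0.38 | 42% | 38% | 222 |

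The difference detectable with 80% power at 45 per arm, solved with the t distribution, is 12.3 points (SD 20.65) to 13.5 points (SD 22.6).

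If the sham SD of 15 is accepted as a genuine CAPS-5 figure and only the acupuncture SD is rescaled (13.95 × 1.569 = 21.9), the pooled SD is √((21.9² + 15²)/2) = 18.8 and power is about 57%.

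**5. Baseline adjustment.** The planned model adjusts for baseline severity but no correlation is stated. The residual SD is SD × √(1 − r²). For 8.5 points at 45 per arm, SD 20.65 to 22.6:

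- r = 0.5: residual SD 17.9 to 19.6, power 61% to 53%.
- r = 0.7: residual SD 14.7 to 16.1, power 77% to 70%.
- r needed for 80%: about 0.72 to 0.78.

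**6. The 12-point scenario.** With pooled SD 20.65 to 23.5 (the upper value is 15 × 1.569), unadjusted power at 45 per arm is 78% to 67%. Total N for 80% is 94 to 122, against the 50 stated.

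**The case against.** The strongest defence is that proportional scaling of the SD is itself an assumption. CAPS-5 is a structured interview and a different instrument, not the PSS-SR stretched, and the documents report no CAPS-5 SD. The entry rule (score of at least 26, relatively homogeneous sample) could narrow the baseline spread. A normal distribution with mean 50 and SD 15.8 (10.1 × 1.569), cut to 26–80, has an SD of about 12.7. This stands as a reason not to treat 21.9 or any other rescaled value as the true SD. It does not rescue the post-treatment 14.4, because the pilot is the plan's only SD evidence and the plan scaled the pilot mean in just this way.

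Two further points stand. The planned analysis adjusts for baseline, so unadjusted power understates what it could achieve. The sample-size table also lists an SD of 20 (162 patients for 8.5 points, 86 for 12), although the stated conclusions do not use those rows.

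Three stronger readings are tempting. A reader might infer an upper limit of 54% for unadjusted power by using the rescaled wait-list SD (12.33 × 1.569 = 19.3) for both arms. The acupuncture arm's rescaled SD is 21.9, so 19.3 is not a pooled value. A reader might infer that the 12-point scenario fails altogether. Only the claim that 50 patients suffice fails: 90 are to be enrolled, and power there is about 67% to 78% before adjustment. A reader might also infer that the trial is shown to be underpowered. The documents do not establish the CAPS-5 SD, so they show only that the claimed power is unsupported.

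**Conclusion.** The concern holds in this form: the mean was rescaled and the SD was not, no CAPS-5 source is given for the SD, and the plan's within-group d departs from the pilot's by about the ratio of the two scales. The stated effect sizes and the 80% power therefore do not follow from the evidence cited.

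For the 8.5-point scenario that sets N = 90, the like-for-like unadjusted power is about 42% to 49%, against 79% to 80% on the plan's inputs. That range rests on the SD scaling by 80/51. Accepting the sham SD of 15 as it stands, or crediting baseline adjustment, moves power upward, but 80% would need a baseline correlation above 0.7 that the plan does not state. The finding concerns the justification of the sample size, not the validity of the primary comparison.

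**What to change.** In the power sections of both documents, do one of two things: support the assumed SD with CAPS-5 data, or put it on the same scale as the mean and show results over a range of SDs. Then restate:

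- the within-group and between-group d;
- power with 90 and with 80 patients, for 8.5 and for 12 points;
- the difference detectable with 80% power.

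Give these for the baseline-adjusted analysis, with the assumed correlation stated and varied. Withdraw or qualify the adequacy statement under Participants and sampling in the Protocol, and the statement in both documents that 50 patients would be more than enough for 12 points.

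The cost is a revision of wording and figures in two documents, and probably a less favourable stated power. No additional patients and no change to trial conduct are requested.
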